#### 13.4 Radiology correlative studies

Patients who undergo CT imaging for tumor response assessment will have their images analyzed by a designated sarcoma radiologist who will be blinded to patient clinical outcome and phase of treatment according to Choi criteria.

Patients who undergo MRI evaluation for tumor response assessment will have dynamic contrast enhancement (DCE) protocol added to the standard sequences obtained. The patient may experience a slightly longer duration in the scanner for these purposes. The outcomes based on DCE imaging will also be analyzed by the designated sarcoma radiologist who will be blinded to patient clinical outcome and phase of treatment. Tumor volume will be calculated using MRI volumetrics in a blinded fashion and analyzed for correlation with RECIST response.

PET/CT scans will be obtained at Screening, Cycle 3 (day 1) and End-of-Treatment visits, to assess metabolic response which may precede radiographic response. If the patient does not have a positive PET/CT at baseline, subsequent scans will be cancelled.

### 13.5 Calendar of Specimen Collection for Correlative Studies

Timepoints	Tumor biopsies	Tumor/TIL analysis (IHC/flow cytometry)	Circulating Tumor Cells (CTCs)	Circulating lymphocyte analysis (flow cytometry)	PET/CT
Screening	X	X			X
Cycle 1, day 1 (predose)			X	X	
Cycle 1, day 8				X	
Cycle 3, day 1 (predose)	X	X	X	X	X
End of Treatment	X	X	X	X	X

**Table 13. Correlative Studies' Timepoints**

### 13.6 Banking of Additional Specimens

In the event that study treatment results in a clinical response to the degree of permitting surgical resection, we will obtain any surgical specimens from patients who opt to withdraw from the study and undergo surgery.

Tumor tissue will be collected and analyzed as follows:

1. Immunohistochemistry for immunomodulatory markers after formalin fixation,
2. Fresh tissue will be transported to the [name] lab for tumor-infiltrating lymphocyte extraction and flow cytometry. TILs will be banked in RNA later for RNA expression analysis using Archer DX platform to determine T cell clonality.
3. Excess tumor tissue will be placed in RNA and frozen for later use.

## 14.0 MEASUREMENT OF EFFECT

### 14.1 Antitumor Effect in Solid Tumors

For the purposes of this study, patients should be re-evaluated for response every 12 weeks (84 days, ±7 days) from date of Enrollment, (while on treatment and until there is documented evidence of disease progression for those patients who come off treatment). Imaging studies should be timed to coincide with the end of the prior treatment cycle, assessing all known sites of disease using the same type(s) of scan(s) that was/were performed at baseline. Response assessments during follow-up after disease progression should follow the same frequency (every 12 weeks, ±7 days).

Response and progression will be evaluated in this study using the international criteria proposed by the revised Response Evaluation Criteria in Solid Tumors (RECIST) version 1.1 guideline(s). Changes in the largest diameter (unidimensional measurement) of the

tumor lesions and the shortest diameter in the case of malignant lymph nodes are used in the RECIST criteria.

The following general principles must be followed:

1. To assess objective response, it is necessary to estimate the overall tumor burden at baseline to which subsequent measurements will be compared. All baseline evaluations should be performed as closely as possible to the beginning of treatment and never more than four weeks before registration.
2. Measurable disease is defined by the presence of at least one measurable lesion.
3. All measurements should be recorded in metric notation by use of a ruler or calipers.
4. The same method of assessment and the same technique must be used to characterize each identified lesion at baseline and during follow-up.

#### 14.1.1 Definitions

##### Evaluable for Objective Response

Only those eligible patients who have measurable disease present at baseline, have received at least one cycle of therapy, and have had their disease re-evaluated will be considered evaluable for response. These patients will have their response classified according to the definitions stated below. (Note: Patients who exhibit objective disease progression prior to the end of cycle 1 will also be considered evaluable.)

##### Evaluable for Toxicity

All eligible patients who receive at least 80% of scheduled doses of axitinib during weeks 1-4, and receive pembrolizumab during week 2. Patients who withdraw from the study prior to week 2 for any reason other than DLT or other significant toxicity will not be considered evaluable for toxicity

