### 3.2 Secondary endpoints

- The objective response (CR/PR), clinical benefit (CR/PR/SD), time to progression (TTP), and overall survival (OS) defined as time from study treatment initiation to first occurrence of progression by RECIST v1.1 or death of sarcoma patients treated with concurrent axitinib/pembrolizumab therapy.

Evaluable criteria:

Eligible subjects enrolled into the study that received at least 80% of scheduled axitinib doses and two infusions of pembrolizumab, have measurable disease at baseline and at least one post-baseline disease assessment.

- Adverse events, including dose-limiting toxicity and serious adverse events (grade 3 or 4) will be graded using NCI CTCAE version 4.03.

Evaluable criteria:

Eligible subjects enrolled into the study that receive at least one dose of both axitinib and pembrolizumab. Patients who withdraw from the study prior to week 2 for any reason other than DLT or other significant toxicity will not be considered evaluable for toxicity.

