**Study treatment must be initiated within seven (7) days of enrollment.**

## 7.0 STUDY DESIGN

The study will be a single-institution, open-label, single-arm phase II study. Since the primary endpoint is survival outcome (PFS) sample size calculation is based on a single-arm survival design. We will employ early stopping rules for lack of efficacy, based on previously reported historical controls (19% PFS at 3 months) and a large database suggesting that a progression-free rate at 3 months of >40% correlates with an active drug in the second-line setting for patients with advanced sarcoma (43). Patients will be treated with twice daily dosing of axitinib alone for the first 7 days, followed by concurrent axitinib administered twice daily at 5 mg PO twice daily, plus intravenous administration of pembrolizumab every 21 days (Figure 3). Patients will be assessed every three weeks for toxicity. After the first five patients are enrolled, we will assess safety of the combination. If 2 or fewer patients exhibit DLT, we will

then proceed with inpatient titration of axitinib dosing at each cycle based on the presence or absence of predefined toxicities (Section 7.1, Table 3). Correlative studies characterizing T-cells in tumor tissue and in peripheral blood will be performed at three timepoints: 1. pre-treatment, 2. on-treatment on cycle 3 day 1, and 3. off-study. Additional exploratory imaging investigations, and assessment of circulating tumor cells are included for all patients (See Appendix F for complete description of correlative studies).

**Figure 3. Schematic diagram of the study.** The first cycle of treatment will be seven weeks, with one week of axitinib alone prior to initiation of pembrolizumab. Subsequently, six-week cycles of treatment consist of twice daily oral doses of axitinib administered continuously with intravenous (I.V.) administration of pembrolizumab on day 1 and 22. The first five evaluable patients will be considered a safety lead-in, and will not have axitinib dose escalation above 5 mg PO bid. If 2 or fewer patients in the safety lead-in develop DLT, axitinib will then be individually titrated based on toxicity beginning on cycle 2 day 1.

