### 16.2 Definitions and Endpoints

#### Analysis set

Analysis set: The analysis set for evaluation of treatment response consists of all study-eligible patients who receive at least 80% of scheduled axitinib doses and two infusions of pembrolizumab, have measurable disease at baseline and at least one post-baseline disease assessment. The analysis set for the second endpoint of toxicity will include all study-eligible patients who receive at least one dose of both drugs.

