### Early stopping guidelines

We propose the following guidelines for the DSMC in its review of accumulating data on toxicity and response. The proposed guidelines were developed using Bayesian methods, which can be applied at any stage of enrollment without advance specification of the number of interim analyses to be performed, or the number of patients evaluable for toxicity, or response, at the time such assessments are made (45, 46).

Under the Bayesian method, we assign a prior probability (level of belief at the start of the trial) to a range of possible values for the true toxicity rate, and likewise for the true response rate. As data on treated patients become available, each of these probability distributions is revised and the resulting posterior probability becomes the basis for recommending either early termination or continuation of the study.

Early stopping rule is applied to 30 patients who receive concurrent axitinib with pembrolizumab. Details are given in the remainder of this section.

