### Early stopping due to safety

If a treatment-related (possible, probable, or definite) death occurs, enrollment will be suspended and continuation of the study will be reassessed by the DSMC.

If four out of first five treated patients experiences DLT then the study will be suspended and reviewed with the Data Safety Monitoring Committee for consideration of modification or

termination. It is based on Bayesian stopping rule that DLT rate should not exceed 40% with a posterior probability of 90% or higher.

For purposes of safety monitoring, we define an unacceptable toxicity to be any treatment-related DLT, where acute refers to the period of time from start of study treatment to one month following completion or discontinuation of treatment. Unacceptable toxicity is expected to occur in no more than 30% of study patients. Early stopping (suspension and possibly termination) will be considered if there is evidence that the proportion of patients experiencing unacceptable toxicity exceeds 40%. Specifically, we suggest as a guideline for early termination a posterior probability of 90% or higher that the rate of unacceptable toxicity exceeds 40%.

The table below shows specific instances where this guideline is met, thus suggesting early termination due to evidence of excessive toxicity.

Number of patients with DLT among 30 patients	Total patients evaluated	Observed toxicity rate
4	4 to 5	≥ 80%
5	6 to 7	≥ 71%
6	8 to 9	≥ 67%
7	10 to 11	≥ 64%
8	12 to 13	≥ 62%
9	14 to 15	≥ 60%
10	16 to 17	≥ 58%
11	18 to 19	≥ 57%
12	20 to 21	≥ 54%
13	22 to 24	≥ 54%
14	25 to 26	≥ 54%
15	27 to 28	≥ 53%
16	29	≥ 55%

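### Section 17 does not name the population its DLT boundary counts, the two toxicity-evaluable definitions conflict, and no boundary is printed for the expansion patients

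*Combined protocol and SAP*

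**What the plan says.** **Two definitions.** Section 3.2 takes as evaluable for toxicity "Eligible subjects enrolled into the study that receive at least one dose of both axitinib and pembrolizumab". Section 16.2 uses the same dose criterion: "The analysis set for the second endpoint of toxicity will include all study-eligible patients who receive at least one dose of both drugs". Section 14.1.1 is stricter: "All eligible patients who receive at least 80% of scheduled doses of axitinib during weeks 1-4, and receive pembrolizumab during week 2". Both 3.2 and 14.1.1 then class as not evaluable "Patients who withdraw from the study prior to week 2 for any reason other than DLT or other significant toxicity", which by implication keeps patients who withdraw that early because of a DLT. Section 16.2 has no such clause.

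**The term in Section 17.** The introduction to the guidelines says the Bayesian method needs no advance fixing of the number of looks "or the number of patients evaluable for toxicity, or response, at the time such assessments are made". The same subsection applies the rule to 30 patients receiving both drugs concurrently. The lead-in rule reads "If four out of first five treated patients experiences DLT then the study will be suspended". The table counts patients evaluated, and its worked example counts patients assessed. For the lead-in, Section 7.0 says "After the first five patients are enrolled, we will assess safety of the combination" in the body and "The first five evaluable patients will be considered a safety lead-in" in the Figure 3 legend.

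**Scope.** The table header refers to 30 patients and the last row is 16 DLTs at n = 29. Section 1.5 reports that the first 30 are accrued and adds up to 10 patients with ASPS for further safety and efficacy data. Section 16.4 now plans on 40 evaluable patients.

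**The concern.** A DLT boundary needs a defined numerator and denominator. Section 14.1.1 filters on exposure in the weeks when a DLT is likely to interrupt exposure, so the event being counted can itself cause exclusion. Removing a patient with a DLT takes one from both counts, and (D - 1)/(N - 1) is below D/N whenever D < N, so the error runs downward. The protocol makes such interruptions plausible. Section 7.2 counts liver function abnormality above 5 x ULN as a DLT, the axitinib modification table holds the drug for grade 2/3 liver enzyme elevation, and Section 11.0 lists a DLT among reasons for stopping treatment.

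The second issue is reach. The expansion is meant to add safety data, but the printed boundary ends before it begins.

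**Working it through.** **1. Exposure threshold in 14.1.1.** Twice-daily axitinib over 28 days is 56 doses, and 0.80 x 56 = 44.8. Missing 11 doses leaves 45/56 = 80.4% (kept). Missing 12, a six-day hold, leaves 44/56 = 78.6% (dropped). This assumes that held doses remain scheduled doses, which the text does not settle.

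**2. Who drops out on a literal reading.**

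| Patient with a DLT | 14.1.1 | 16.2 |
|---|---|---|
| Stays on study, axitinib held 6 days or more in weeks 1-4 | dropped | counted |
| Stays on study, week-2 pembrolizumab not given, given later | dropped | counted |
| DLT in the axitinib-only week, never receives pembrolizumab, withdraws before week 2 | kept by implication of the withdrawal clause | dropped |
| As above but does not withdraw before week 2 | dropped | dropped |

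**3. Reproducing the plan's table.** Prior Beta(0.6, 1.4); after x DLTs in n patients the posterior is Beta(0.6 + x, 1.4 + n - x); stop when P(rate > 0.40) is at least 0.90. The prior probability above 0.40 is 0.320, matching the stated 32%. The printed boundaries are reproduced at 25 of the 26 values of n from 4 to 29. The exception is n = 24: 13/24 gives 0.896, below 0.90 (it passes only if rounded to two decimals), and 14/24 gives 0.952.

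**4. Size of an exclusion.** The number of patients dropped is illustrative; the documents give none.

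| All treated | Posterior | DLT patients dropped | Remaining | Posterior |
|---|---|---|---|---|
| 12/20 (60.0%) | 0.949 | 1 | 11/19 (57.9%) | 0.920 |
| 12/20 (60.0%) | 0.949 | 2 | 10/18 (55.6%) | 0.878 |
| 16/30 (53.3%) | 0.911 | 1 | 15/29 (51.7%) | 0.875 |

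The opposite error is also possible. Adding one under-exposed patient without a DLT to 4/5 (0.920) gives 4/6 (0.842).

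**5. Carrying the same rule to 40.** Smallest x reaching 0.90, with the posterior at the last n of each row:

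| n | DLTs | Posterior at last n |
|---|---|---|
| 30 | 16 | 0.911 |
| 31-32 | 17 | 0.916 |
| 33-34 | 18 | 0.920 |
| 35-37 | 19 | 0.901 |
| 38-39 | 20 | 0.906 |
| 40 | 21 | 0.932 |

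**6. Operating characteristics.** Exact binomial recursion, printed table to 29 against the same table plus these rows to 40. The plan sets no look schedule, so two are shown.

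| True DLT rate | Look after every patient | Looks at 5, 15, 29, 40 |
|---|---|---|
| 30% | 6.9% to 7.1% | 4.3% to 4.4% |
| 40% | 26.0% to 29.0% | 17.6% to 19.7% |
| 50% | 60.2% to 68.5% | 48.5% to 57.4% |
| 60% | 89.0% to 94.7% | 82.9% to 91.2% |

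These run from the first patient and do not condition on the 30 already observed.

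**The case against.** The strongest reply is that Section 17 never adopts 14.1.1. The phrase evaluable for toxicity occurs there once, in a general sentence about Bayesian monitoring. The operative words are patients receiving both drugs, treated and evaluated, and 14.1.1 sits under antitumor effect. That stands: the defect is an unnamed population, not a rule tied to the stricter definition.

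A reader might infer that the conflict reverses the lead-in decision, since 4/5 gives 0.920 and 3/4, with one DLT patient dropped, gives 0.842. The lead-in rule counts the first five treated, which largely answers this, and with 30 accrued the early looks are past. A reader might also infer that it reverses a decision in the expansion. Reversals beyond n = 29, such as the 16/30 case, need a boundary the plan has not printed.

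On reporting, Section 16.3 already summarises the number treated and the number with DLT, which limits the effect on the final report. On scope, the 90% criterion can be applied at any stage of enrollment, suspension after a treatment-related death is not capped at 30, and DSMC review continues. The guidelines are offered for DSMC consideration only.

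None of this tells the DSMC which patients form the denominator, or gives it a printed boundary past 29.

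**Conclusion.** The concern holds as unreconciled wording with a plausible direction of bias. The definitions select different patients, and on a literal reading each can exclude someone because of the DLT being counted. For 14.1.1 the dose-hold route assumes that held doses count as scheduled. How many patients are affected cannot be determined from the documents, and they do not support a claim that DLTs have been lost or that an earlier stopping decision was wrong.

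The expansion has no printed DLT boundary, but it is not without safety oversight. At the expected 30% rate the missing rows change the chance of stopping by about 0.1-0.2 points; at 50% by about 8-9 points, under the two look schedules shown. The practical effect is on the expansion and the final toxicity report.

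**What to change.** - Use one toxicity set in 3.2, 14.1.1, 16.2 and 17 in which every treated patient with a DLT counts, whatever dose was received. State how under-exposed patients without a DLT are handled, since including them lowers the observed rate. Use one term for the lead-in five.
- Extend the table to 40 with the rows in step 5, and move n = 24 to the 14-DLT row.
- Minor clean-up: reconcile the 49-day DLT window in 7.2 with the acute window in Section 17, which is defined but not used. Recheck the printed rates: 12/21 is 57%, not 54%; 10/17, 11/19 and 15/28 round to 59%, 58% and 54%.

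The cost is protocol wording and six table rows from the plan's own prior. With a look after every patient, stopping becomes more likely by about 0.2 points at a true rate of 30% and about 8 points at 50%.

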#### 14.1.2 Disease Parameters

##### Measurable Disease

Measurable lesions are defined as those that can be accurately measured in at least one dimension (longest diameter to be recorded) as  $\geq 20$  mm by chest x-ray, as  $\geq 10$  mm with CT scan, or  $\geq 10$  mm with calipers by clinical exam. All tumor measurements must be recorded in millimeters (or decimal fractions of centimeters).

**NOTE:** Tumor lesions that are situated in a previously irradiated area may be considered measurable if they have grown subsequent to previous radiation.

##### Malignant Lymph Nodes

To be considered pathologically enlarged and measurable, a lymph node must be  $\geq 15$  mm in **short** axis when assessed by CT scan (CT scan slice thickness

recommended to be no greater than 5 mm). At baseline and in follow-up, only the **short** axis will be measured and followed.

#### Non-measurable Disease

All other lesions (or sites of disease), including small lesions (longest diameter < 10 mm or pathological lymph nodes with  $\geq 10$  to < 15 mm short axis), are considered non-measurable disease. Bone lesions, leptomeningeal disease, ascites, pleural/pericardial effusions, lymphangitis cutis/pulmonitis, inflammatory breast disease, and abdominal masses (not followed by CT or MRI), are considered as non-measurable. Non-measurable also includes lesions that are < 20 mm by chest x-ray.

NOTE: Cystic lesions that meet the criteria for radiographically defined simple cysts should not be considered as malignant lesions (neither measurable nor non-measurable) since they are, by definition, simple cysts.

‘Cystic lesions’ thought to represent cystic metastases can be considered as measurable lesions, if they meet the definition of measurability described above. However, if non-cystic lesions are present in the same patient, these are preferred for selection as target lesions.

#### Target Lesions

All measurable lesions up to a maximum of 2 lesions per organ and 5 lesions in total, representative of all involved organs, should be identified as target lesions and recorded and measured at baseline. Target lesions should be selected on the basis of their size (lesions with the longest diameter), be representative of all involved organs, but in addition should be those that lend themselves to reproducible repeated measurements. It may be the case that, on occasion, the largest lesion does not lend itself to reproducible measurement in which circumstance the next largest lesion which can be measured reproducibly should be selected.

A sum of the diameters (longest for non-nodal lesions, short axis for nodal lesions) for all target lesions will be calculated and reported as the baseline sum diameters. If lymph nodes are to be included in the sum, then only the short axis is added into the sum. The baseline sum of the diameters will be used as reference to further characterize any objective tumor regression in the measurable dimension of the disease.

#### Non-target Lesions

All other lesions (or sites of disease) including any measurable lesions over and above the 5 target lesions should be identified as **non-target lesions** and should also be recorded at baseline. Measurements of these lesions are not required, but the presence or absence of unequivocal progression of each should be noted throughout follow-up.

#### 14.1.3 Methods for Evaluation of Disease

All measurements should be taken and recorded in metric notation using a ruler or calipers. All baseline evaluations should be performed as closely as possible to the beginning of treatment and never more than 4 weeks (28 days) before enrollment.

The same method of assessment and the same technique must be used to characterize each identified and reported lesion at baseline and during follow-up. Imaging-based evaluation is preferred to evaluation by clinical examination unless the lesion(s) being followed cannot be imaged but are assessable by clinical exam.

##### Clinical Lesions

Clinical lesions will only be considered measurable when they are superficial (e.g., skin nodules and palpable lymph nodes) and  $\geq 10$  mm in diameter as assessed using calipers (e.g., skin nodules). In the case of skin lesions, documentation by color photography, including a ruler to estimate the size of the lesion, is recommended.

##### Chest X-ray

Lesions on chest x-ray are acceptable as measurable lesions when they are clearly defined and surrounded by aerated lung. However, CT is preferable since it is considered more sensitive.

